## **Data Analysis Plan For Demographic/Clinical Characteristics and Serology Data**

---

**Objective:** To compare the serum antibody responses to HPV 6, 11, 16 and 18 at 7 and 30 days post-booster dose of HPV vaccine in females that received either a primary 2 or 3 dose series of Q-HPV vaccine 8-10 years ago.

**Primary testing** is to determine non-inferiority (95% CI, lower bound  $>0.5$ ) of geometric mean titer (GMT) ratios for anti-HPV 6, 11, 16, 18 for 2-dose girls compared with 3-dose girls and 3-dose women.

Co-primary endpoints are the antibody levels measured by MERCK using competitive Luminex immunoassay (cLIA) at 7 and 30 days post-booster dose of HPV vaccine.

Co-secondary endpoints are the antibody levels measured by MERCK using total IgG Luminex immunoassay (TIgG) at 7 and 30 days post-booster dose of HPV vaccine. Antibody levels measured by cLIA and TIgG at baseline will also be compared in the three groups.

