2.0 OBJECTIVES

Primary objective:

- To compare the B memory and plasmablast populations between girls and young women that received either a primary 2 or 3 dose series, who are then challenged with a subsequent dose after 120 months.

Secondary objectives:

- To compare the extent of somatic hypermutation and the variable gene usage between girls that received either a primary 2 or 3 dose series.
- To compare the serum antibody responses to HPV 6, 11, 16 & 18 at month 120 in females that received either a primary 2 or 3 dose series, who are then challenged with a subsequent dose.

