#### **Non-inferiority testing:**

To test non-inferiority, t-test will be applied to assess GMT ratios in different groups (2-dose girls vs. 3-dose girls; 2-dose girls vs. 3-dose women; 3-dose girls vs. 3-dose women) at 7 and 30 days post-booster dose of HPV vaccine. Non-inferiority will be declared if the lower bound of the 95% confidence interval (95% CI) of GMT ratios is greater than 0.5 (Table 2-3).

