## Figures and Tables:

Figure 1. Study participation consort diagram to summarize enrollment, withdraw, loss of follow-up, eligibility...

[figure not shown]

Table 1. Demographic/clinical characteristics of the study population

Characteristics	Group 1 (2-dose girls)		Group 2 (3-dose girls)		Group 3 (3-dose women)	
	N	%	N	%	N	%
Age at enrollment, mean (SD), year						
Age at first dose of Q-HPV vaccine, mean (SD), year						
Weight, mean (SD), kg						
BMI, mean (SD)						
Ethnicity						
White						
Chinese						
Other						
Health history						
Immunization history						

**Group 1:** girls who received 2 doses of Q-HPV vaccine at 0, 6 month schedule 8-10 years ago when they were between 9-13 years of age at the time of the first dose

**Group 2:** girls who received 3 doses of Q-HPV vaccine at 0, 2, 6 month schedule 8-10 years ago when they were between 9-13 years of age at the time of the first dose

**Group 3:** young women who received 3 doses of Q-HPV vaccine at 0, 2, 6 month schedule 8-10 years ago when they were between 16-26 years of age at the time of the first dose)

Table 2. Summary of anti-HPV GMTs at baseline, and 7 and 30 days post-booster dose (cLIA)

Antibodies (cLIA)	Group 1 (2-dose girls)		Group 2 (3-dose girls)		Group 3 (3-dose women)		GMT ratio (95% CI)		
	n	GMT (95% CI)	n	GMT (95% CI)	n	GMT (95% CI)	2-dose girl/3-dose girl	2-dose girl/3-dose women	3-dose girl/3-dose women
Baseline									
HPV 6									
HPV 11									
HPV 16									
HPV 18									
At 7 days post-booster dose									
HPV 6									
HPV 11									
HPV 16									

HPV 18									
At 30 days post-booster dose									
HPV 6									
HPV 11									
HPV 16									
HPV 18									

Table 3. Summary of anti-HPV GMTs at baseline, and 7 and 30 days post-booster dose (total IgG)

Antibodies (IGG)	Group 1 (2-dose girls)		Group 2 (3-dose girls)		Group 3 (3-dose women)		GMT ratio (95% CI)		
	n	GMT (95% CI)	n	GMT (95% CI)	n	GMT (95% CI)	2-dose girl/3-dose girl	2-dose girl/3-dose women	3-dose girl/3-dose women
Baseline									
HPV 6									
HPV 11									
HPV 16									
HPV 18									
At 7 days post-booster dose									
HPV 6									
HPV 11									
HPV 16									
HPV 18									
At 30 days post-booster dose									
HPV 6									
HPV 11									
HPV 16									
HPV 18									

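### Does the SAP need a rule for combining its 16 (or 24) cLIA non-inferiority ratios into one claim?

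*SAP*

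**What the plan says.** The SAP is confined to part of the trial by its title, "Data Analysis Plan For Demographic/Clinical Characteristics and Serology Data". Its statement of primary testing concerns GMT ratios for HPV 6, 11, 16 and 18 "for 2-dose girls compared with 3-dose girls and 3-dose women". It then names the endpoints: "Co-primary endpoints are the antibody levels measured by MERCK using competitive Luminex immunoassay (cLIA) at 7 and 30 days" after the booster. Total IgG levels are co-secondary.

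The SAP section on non-inferiority testing describes the t-test for GMT ratios. Its list of contrasts ends with "3-dose girls vs. 3-dose women) at 7 and 30 days post-booster dose of HPV vaccine", and its criterion reads: "Non-inferiority will be declared if the lower bound of the 95% confidence interval (95% CI) of GMT ratios is greater than 0.5". It refers to Tables 2-3, so it covers both assays. It does not use the word primary.

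In the protocol (2.0 Objectives) the primary objective is "To compare the B memory and plasmablast populations between girls and young women". Serology is a secondary objective: "To compare the serum antibody responses to HPV 6, 11, 16 & 18 at month 120 in females". Protocol 3.0 sets 6 participants per group.

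**The concern.** Two things stand out. First, the number of primary ratios seems to depend on which SAP section is read: 16 from the opening statement, 24 if the third contrast counts. Second, the plan calls several endpoints co-primary without saying whether all, some or any of them must meet the margin before a comparison is called non-inferior. There is no hierarchy and no adjustment.

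If one favourable ratio among many could support an overall statement that 2-dose girls are non-inferior, the error rate of that statement would be well above 2.5%. With 6 per group, some ratios will often pass and others fail even when the groups are equal, so the meaning of a split result might be settled after seeing it.

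**Working it through.** **Inputs from the documents:** 4 HPV types; 2 post-booster days; 2 comparisons in the primary statement and 3 in the non-inferiority section; margin 0.5; lower limit of a two-sided 95% CI; 6 per group. **Assumed, because the documents give neither:** natural-log SD of 0.6 or 1.0, and a common correlation between the eight endpoints of a comparison from 0 to 0.9. The plan states no power or family-wise error figure to reproduce.

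**Counts.** Primary statement: 4 × 2 × 2 = 16 cLIA ratios. Non-inferiority section: 4 × 2 × 3 = 24 for cLIA, and 48 with total IgG. The figure of 24 takes the cLIA restriction from the opening section but drops that section's restriction to two comparisons. Keeping both gives 16 primary ratios and 8 supplementary ones.

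**Error per ratio.** The lower limit of a two-sided 95% CI gives 2.5% one-sided error for each declaration.

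**Error if any one pass sufficed (hypothetical).** With independent ratios all at 0.5:
- 8 ratios: 1 − 0.975^8 = 18.3%
- 16 ratios: 1 − 0.975^16 = 33.3%

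Simulation (40,000 runs, pooled t with 10 df, critical value 2.228, shared 2-dose group) gives the first two rows of the table below. All 24 ratios cannot sit at the margin together: if 2-dose/3-dose girls and 3-dose girls/3-dose women are both 0.5, then 2-dose girls/3-dose women is 0.5 × 0.5 = 0.25.

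**Chance that one ratio passes at a true ratio of 1.** The standard error is SD × √(2/6), and the noncentrality is ln 2 divided by it.
- SD 0.6: 0.693/0.346 = 2.00, pass chance 44.0%
- SD 1.0: 0.693/0.577 = 1.20, pass chance 19.2%

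**Mixed result (1 to 7 of 8 pass) at a true ratio of 1.** With independence:
- SD 0.6: 1 − 0.56^8 − 0.44^8 = 99%
- SD 1.0: 1 − 0.808^8 − 0.192^8 = 82%

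| Correlation | 0 | 0.3 | 0.5 | 0.7 | 0.9 |
|---|---|---|---|---|---|
| Any of 8 passes, all at 0.5 (%) | 18.6 | 15.7 | 13.4 | 10.4 | 6.5 |
| Any of 16 passes, all at 0.5 (%) | 31.3 | 26.7 | 22.3 | 17.5 | 11.4 |
| Mixed, true ratio 1, SD 0.6 (%) | 99 | 91 | 80 | 65 | 39 |
| Mixed, true ratio 1, SD 1.0 (%) | 82 | 68 | 58 | 46 | 27 |
| All 8 pass, true ratio 1, SD 0.6 (%) | 0 | 2 | 7 | 13 | 25 |
| All 8 pass, true ratio 1, SD 1.0 (%) | 0 | 0 | 1 | 3 | 8 |

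**What a written rule would do.** Requiring all eight ratios holds the error at about 2.5% per comparison in the worst case (one ratio at 0.5, seven far above), and at about 4.5% for either comparison. Requiring only the four Day 30 ratios has the same 2.5% worst case, and is met in 4–30% (SD 0.6) or 0–10% (SD 1.0) of trials with equal groups. Neither rule alters an estimate, an interval or the chance of a mixed result.

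**The case for a change.** The best argument for a change is that a split result is likely under every assumption tried: even at correlation 0.9 it occurs in 27–39% of trials with equal groups. Co-primary often means that all endpoints must be met, but the SAP does not say so, and it uses co-secondary in the same way. A short statement made beforehand would remove the doubt at almost no cost.

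The facts in that argument stand. No overall rule is written, and the third contrast is not labelled. The inference to a defect does not stand. The SAP announces no overall claim, so no declared error rate is breached. Table 2 has a cell for each of the 24 post-booster cLIA ratios with its CI, so a split cannot be hidden by selection. If co-primary is read as all must pass, the error for a comparison is again about 2.5%.

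The choice of rule would be a matter of preference. The all-eight and Day 30-only conditions are both defensible, and both would usually fail when the groups are equal.

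A related worry is that protocol 4.8.2 retains participants with no Day 7 blood. The tables already carry an n column for each group, type and day. Losing one sample (5 against 6) lowers the single-ratio pass chance only from 44.0% to 39.9% at SD 0.6, and from 19.2% to 17.5% at SD 1.0.

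**Conclusion.** No change to the plan follows. The apparent conflict between 16 and 24 ratios is a gap in labelling: the opening section defines the primary tests, and the later section gives the method for every GMT-ratio contrast in both assays. An analyst who follows the SAP as written reports each ratio with its 95% CI and declares non-inferiority ratio by ratio at 2.5% one-sided error, which is sound. The natural reading of the third contrast is supplementary. The title and Objective confine the word primary to the serology plan, so it does not compete with the protocol's ranking of objectives.

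The inflated error rates (6.5–18.6% within a comparison, 11.4–31.3% over both) are hypothetical, since they need an any-one-pass rule that the SAP does not contain. The 27–99% range for a mixed result rests on assumed SDs and correlations. It reflects 6 participants per group, which a combining rule would not alter. Such a rule would only record one of several acceptable interpretations, for a secondary objective in a trial of 18 participants.

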### **Statistical Analysis:**

### **Participation and demographic/clinical Characteristics:**

Descriptive analysis (i.e. frequency and/or percentage) will be used to summarize study population, including enrollment, withdraw, loss to follow-up, eligibility (Figure 1); and demographic/clinical characteristics including age, baseline health and immunization history (Table 1).

### **Evaluation of anti-HPV antibody levels:**

Merck employed cLIA and TIgG to measure neutralizing and total IgG antibody response to 9-valent HPV vaccine. To assess anti-HPV antibody levels, we will use the results of cLIA and total IgG at baseline (visit 1), and at 7 days (visit 2) and 30 days (visit 3) post-booster dose of HPV vaccine. GMTs of anti-HPV 6, 11, 16, and 18 antibodies will be computed for each group at the three time points. To allow GMT calculation, samples with undetectable anti-HPV will be assigned the half of the lowest detectable value (cLIA: *HPV6, 2 mMU/ml; HPV11, 3 mMU/ml; HPV16, 5 mMU/ml; HPV18, 10 mMU/ml.* TIgG: *HPV6, 2 mIU/ml; HPV11, 3 mIU/ml; HPV16, 5 mIU/ml; HPV18, 10 mIU/ml.*

*HPV6, 2 mMU/ml; HPV11, 2 mMU/ml; HPV16, 4 mMU/ml; HPV18, 3 mMU/ml).* 95% confidence intervals (CIs) of GMT will be calculated by back transformation of the 95% CI for the log-transformed GMT (Table 2-3).

#### **Non-inferiority testing:**

To test non-inferiority, t-test will be applied to assess GMT ratios in different groups (2-dose girls vs. 3-dose girls; 2-dose girls vs. 3-dose women; 3-dose girls vs. 3-dose women) at 7 and 30 days post-booster dose of HPV vaccine. Non-inferiority will be declared if the lower bound of the 95% confidence interval (95% CI) of GMT ratios is greater than 0.5 (Table 2-3).

#### **Evaluation of seropositivity:**

Seropositivity will be examined for the three groups at baseline, and at 7 and 30 days post-booster dose of HPV vaccine. Positivity thresholds for cLIA are 20 mMU/mL, 16mMU/mL, 20 mMU/mL, and 24 mMU/mL for anti-HPV 6, 11, 16, and 18, respectively; whereas total IgG 15 mMU/mL, 15mMU/mL, 7 mMU/mL, and 10 mMU/mL respectively. A participant is considered to be seropositive if the respective anti-HPV antibody level exceeds or equal to these threshold (Table 4-5). Chi-squared test will be used to compare seropositivity rate in different groups (2-dose girls vs. 3-dose girls; 2-dose girls vs. 3-dose women; 3-dose girls vs. 3-dose women) at baseline, and at 7 and 30 days post-booster dose of HPV vaccine. A margin of 10% of difference in seropositivity rate will be used for non-inferiority testing.

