3.0 STUDY DESIGN AND PARTICIPANT OVERVIEW

This is a single center, interventional study to evaluate long term memory response to HPV 6, 11, 16 & 18. Memory response will be assessed by measuring seroprotection 8-10 years post Q-HPV vaccination and to challenge with a booster dose of HPV9 vaccine (Gardasil® 9, Merck Canada, Inc.) years after the original exposure to measure the long-lasting anamnestic response. This is a 3 arm study with 6 girls per group:

Group 1: girls who received 2 doses of Q-HPV vaccine at 0, 6 month schedule 8-10 years ago when they were between 9-13 years of age at the time of the first dose.

Group 2: girls who received 3 doses of Q-HPV vaccine at 0, 2, 6 month schedule 8-10 years ago when they were between 9-13 years of age at the time of the first dose.

Group 3: young women who received 3 doses of Q-HPV vaccine at 0, 2, 6 month schedule 8-10 years ago when they were between 16-26 years of age at the time of the first dose.

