Table 4. Summary of HPV seropositivity at baseline, and at 7 and 30 days post-booster dose (cLIA)

Antibodies (cLIA)	Group 1 (2-dose girls)			Group 2 (3-dose girls)			Group 3 (3-dose women)		
	n	% seropositive (95% CI)	n	% seropositive (95% CI)	n	% seropositive (95% CI)	n	% seropositive (95% CI)	
Baseline									
HPV 6									
HPV 11									
HPV 16									

HPV 18						
At 7 days post-booster dose						
HPV 6						
HPV 11						
HPV 16						
HPV 18						
At 30 days post-booster dose						
HPV 6						
HPV 11						
HPV 16						
HPV 18						

Table 5. Summary of HPV seropositivity at baseline, and 7 and 30 days post-booster dose (total IGG)

Antibodies (IGG)	Group 1 (2-dose girls)		Group 2 (3-dose girls)		Group 3 (3-dose women)	
	n	% seropositive (95% CI)	n	% seropositive (95% CI)	n	% seropositive (95% CI)
Baseline						
HPV 6						
HPV 11						
HPV 16						
HPV 18						
At 7 days post-booster dose						
HPV 6						
HPV 11						
HPV 16						
HPV 18						
At 30 days post-booster dose						

HPV 6						
HPV 11						
HPV 16						
HPV 18						

Table 6. Difference in anti- HPV GMTs between baseline vs. at 7 and 30 days post-booster dose of HPV vaccine (cLIA)

Antibodies (cLIA)	Group 1 (2-dose girls)		Group 2 (3-dose girls)		Group 3 (3-dose women)		Group 1 vs 2	Group 1 vs 3	Group 1 vs 3
	Log Difference	P Value	Log Difference	P value	Log Difference	P value	P-value for difference between differences for group 1 vs 2	P-value for difference between differences for group vs 3	P-value for difference between differences for group 1 vs 3
Baseline vs. 7 days post-booster dose of HPV vaccine									
HPV 6									
HPV 11									
HPV 16									
HPV 18									
Baseline vs. 30 days post-booster dose of HPV vaccine									
HPV 6									
HPV 11									
HPV 16									
HPV 18									

Table 7. Difference in anti- HPV GMTs between baseline vs. at 7 and 30 days post-booster dose of HPV vaccine (total IgG)

Antibodies (IGG)	Group 1 (2-dose girls)		Group 2 (3-dose girls)		Group 3 (3-dose women)		Group 1 vs 2	Group 1 vs 3	Group 1 vs 3
	Log Difference	P Value	Log Difference	P value	Log Difference	P value	P-value for difference between differences	P-value for difference between differences for group	P-value for difference between differences
Baseline vs. 7 days post-booster dose of HPV vaccine									
HPV 6									
HPV 11									
HPV 16									
HPV 18									
Baseline vs. 30 days post-booster dose of HPV vaccine									

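### The SAP sets a 10-point non-inferiority margin for seropositivity without an interval, level or decision rule, and with 6 per group the margin is very unlikely to be met when the groups are truly equal

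*SAP*

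**What the plan says.** The SAP section on evaluation of seropositivity covers three visits: "Seropositivity will be examined for the three groups at baseline, and at 7 and 30 days post-booster dose of HPV vaccine". For the three pairwise group comparisons it names one test: "Chi-squared test will be used to compare seropositivity rate in different groups". Its last sentence then adds: "A margin of 10% of difference in seropositivity rate will be used for non-inferiority testing". The section says nothing about how the difference is to be estimated, at what confidence level, in which direction, or what result would count as non-inferior.

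The SAP's only declaration rule is in the section on non-inferiority testing, and it is worded for titres: "Non-inferiority will be declared if the lower bound of the 95% confidence interval (95% CI) of GMT ratios is greater than 0.5". SAP Tables 2 and 3 have columns for GMT ratios with confidence intervals. SAP Table 5 has only a per-group percentage with its interval, and no column for a between-group difference or a non-inferiority result.

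The SAP gives no group size. The protocol does, in section 3.0: "This is a 3 arm study with 6 girls per group". Neither document gives an expected seropositivity rate or a sample-size calculation. The opening section of the SAP makes antibody levels by cLIA co-primary and antibody levels by total IgG co-secondary; seropositivity is in neither list.

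**The concern.** A non-inferiority margin has effect only through a rule that compares it with something, usually a confidence limit for the difference. Here the margin stands next to a test that makes no use of it. The null hypothesis of chi-squared is equal rates. A large p-value from it with 6 per group says very little, yet it could be misread as support for non-inferiority. If everyone in both groups is seropositive, the test gives no p-value at all.

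Because the interval is not named, the same data could lead to different statements depending on a choice made later. The margin is also narrower than the data can resolve: with 6 per group, one participant is 1/6 = 16.7 points. What is at stake is a formal supporting claim about 2 against 3 doses, not the primary titre comparison.

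**Working it through.** The documents contain no power or precision figure for this margin, so there is nothing to reproduce.

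**Inputs**
- Margin: 10 points, read as an absolute difference in rates (SAP, evaluation of seropositivity).
- n = 6 per group (protocol 3.0).
- Level: not stated for seropositivity. Two-sided 95% is borrowed from the SAP's GMT rule, and 90% is shown as a sensitivity check.
- Pass rule (assumed): lower limit of tested minus comparator above -0.10.
- True rates: not given, so they are varied.

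**1. Chi-squared at this size.** The expected count for the rarer result in each group is half its total among 12, so at most 6/2 = 3, and 0.5 if one of 12 is negative. At 6/6 against 6/6 the expected number of negatives is zero and the statistic is undefined. The chance of that is p^12: 28% at a true 90% in both groups, 54% at 95%, 78% at 98%.

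**2. Lower limit at 6/6 against 6/6.**
- Newcombe: the Wilson lower limit for n/n is n/(n + z²) and the upper limit is 1, so the limit for the difference is -z²/(n + z²). At 95%, z² = 3.841, giving -3.841/9.841 = -0.390.
- Miettinen-Nurminen: the same form with z² multiplied by N/(N - 1) = 12/11, so 4.191, giving -4.191/10.191 = -0.411.
- At 90%, z² = 2.706: Newcombe -2.706/8.706 = -0.311; Miettinen-Nurminen -2.951/8.951 = -0.330.

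All are far below -0.10.

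**3. All 7 × 7 = 49 outcomes (tested v comparator).**
- At 95%, Newcombe and Miettinen-Nurminen pass the same 10: 6v3, 6v2, 6v1, 6v0, 5v2, 5v1, 5v0, 4v1, 4v0, 3v0. In each the tested group leads by at least 3. Even 6v5 fails (Newcombe lower limit -0.247).
- At 90%, both methods pass 12: the same 10 plus 6v4 and 2v0, so the smallest passing lead is 2.

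**4. Chance of passing at equal true rates.** Sum Bin(x; 6, p) × Bin(y; 6, p) over the passing pairs. At p = 0.5 and 95%, the products of binomial coefficients sum to 20 + 15 + 90 + 6 + 36 + 90 + 1 + 6 + 15 + 20 = 299, and 299/4096 = 7.3%, which is the maximum.

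| Assumed true rate, both groups | 95% interval | 90% interval |
|---|---|---|
| 90% | 0.9% | 6.1% |
| 95% | 0.2% | 2.4% |
| Maximum over all rates | 7.3% | 9.9% |

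**5. Size needed.** With everyone seropositive, Newcombe at 95% needs z²/(n + z²) < 0.10, so n > 9 × 3.841 = 34.6, or 35 per group. Miettinen-Nurminen needs 36. At 90% both need 25.

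**6. Dependence on the unnamed method.** As an illustration only, an uncorrected Wald interval at 6/6 against 6/6 is [0, 0] and would pass automatically.

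**The case against.** The strongest reply is that the SAP uses chi-squared to compare rates and puts the margin in a separate sentence, so it does not actually say that chi-squared is the non-inferiority test. That is fair. The defect is the missing interval and rule; an equality test is not wrong in itself for an equality comparison. But no other method is named, so the margin is left with nothing to operate it.

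A second reply is that the 95% lower-bound rule carries over from the GMT section. At most the level carries over: that rule concerns a ratio above 0.5 and names no interval for a difference in proportions. The level does matter to the figures, which is why 90% is shown. The lead of at least 3 of 6 and the 7.3% ceiling hold at 95% only; the failure at 6/6 against 6/6 holds at both levels.

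A third reply is that preferring Fisher's test to chi-squared is partly taste. This stands. Over the 49 outcomes, uncorrected chi-squared reaches p ≤ 0.05 in 16, with type I error up to 6.8%; Fisher does so in 6, with type I error up to 0.6%. One slightly exceeds its level and the other is very conservative. The point that remains is that a retained test must be defined when all are seropositive.

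Finally, keeping the margin and reporting non-inferiority as not shown would be honest. That is so, provided the rule is written down first.

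**Conclusion.** The concern holds in a limited form. The SAP sets a margin with no interval, level or rule to apply it, and its only named test ignores the margin and is undefined on fully seropositive data. Under either score-type interval, 6/6 against 6/6 does not show non-inferiority at 95% or 90%. The margin can be met only when the tested group is well ahead, and it is very unlikely to be met when the groups are truly equal: at most 7.3% at 95%, or 9.9% at 90%. These figures assume 6 evaluable participants per group, an absolute 10-point margin and a lower-limit rule; the low values at high seropositivity also rest on assumed true rates.

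Three stronger inferences are not supported. A reader might conclude that 6 per group can never meet the margin, but 10 of 49 outcomes do at 95% and 12 at 90%. A reader might expect non-inferiority to be declared automatically on fully seropositive data, but that needs an interval such as Wald, which the SAP does not name. And a reader might think the main serology conclusion is at risk, but seropositivity is neither co-primary nor co-secondary, and the GMT comparison does not depend on it. This should be fixed, but it is a supporting analysis.

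**What to change.** Delete the formal 10% non-inferiority test for seropositivity. In its place, report n/N with exact (Clopper-Pearson) 95% CIs for each group, and the between-group difference with a Newcombe or Miettinen-Nurminen 95% CI, labelled descriptive, in an added column of the seropositivity tables.

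If the margin is kept for transparency, name that score-type interval, its level, the direction (tested minus comparator) and the rule that the lower limit must exceed -10 points. State in advance that 6/6 against 6/6 would be reported as non-inferiority not shown. This closes the gap in wording but keeps a test that rarely passes at equal true rates.

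Any p-value retained should come from a small-sample exact test that is defined when all are seropositive. Fisher's test is one option, and the SAP should say that it is conservative.

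The cost is a few lines of SAP text and one table column; data collection does not change. A formal supporting claim is given up. The Newcombe interval is itself approximate at n = 6 (up to 3.6% false declarations at a true 10-point deficit, against a nominal 2.5%), another reason to present it descriptively. The SAP describes the assays in the past tense but does not date itself against the data; if serology results already existed, the change must be disclosed.
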